3.3 Exclusion Criteria – Arm A

1. Currently receiving or scheduled to receive any other therapies intended to treat the newly diagnosed glioma prior to MLA and the first post-MLA blood collection for correlative studies.
2. Multi-focal or metastatic disease.
3. Pregnant and/or breastfeeding. Premenopausal women must have a negative serum or urine pregnancy test within 14 days of study entry.
4. Inability to undergo MRI due to personal or medical reasons.
5. Known history of HIV or autoimmune diseases requiring immunosuppressant drugs.

3.4 Exclusion Criteria – Arm B

1. Prior treatment with bevacizumab within 12 weeks of study entry.
2. Previous treatment with complete cumulative doses of daunorubicin, idarubicin, and/or other anthracyclines and anthracenediones that is equivalent to a total dose of $> 200 \text{ mg/m}^2$ doxorubicin.
3. More than 2 prior relapses (not counting the current relapse being treated on this study).
4. Currently receiving any other investigational agents that are intended as treatments of the relapsed tumor.

5. Multi-focal or metastatic disease.
6. A history of allergic reactions attributed to compounds of similar chemical or biologic composition to doxorubicin or other agents used in the study.
7. Uncontrolled intercurrent illness including, but not limited to, ongoing or active infection, symptomatic congestive heart failure, unstable angina pectoris, cardiac arrhythmia, recent heart attack within the previous 12 months or severe heart problems, or psychiatric illness/social situations that would limit compliance with study requirements.
8. Pregnant and/or breastfeeding. Premenopausal women must have a negative serum or urine pregnancy test within 14 days of study entry.
9. Inability to undergo MRI due to personal or medical reasons.
10. Known history of HIV or autoimmune diseases requiring immunosuppressant drugs.

3.5 Inclusion of Women and Minorities

Males and females and members of all races and ethnic groups are eligible for this trial.

4.0 REGISTRATION PROCEDURES

Patients must not start any protocol intervention prior to registration through the Siteman Cancer Center.

The following steps must be taken before registering patients to this study:

1. Confirmation of patient eligibility
2. Registration of patient in the Siteman Cancer Center OnCore database
3. Assignment of unique patient number (UPN)

4.1 Confirmation of Patient Eligibility

Confirm patient eligibility by collecting the information listed below:

1. Registering MD's name
2. Patient's race, sex, and DOB
3. Three letters (or two letters and a dash) for the patient's initials
4. Copy of signed consent form
5. Completed eligibility checklist, signed and dated by a member of the study team
6. Copy of appropriate source documentation confirming patient eligibility

4.2 Patient Registration in the Siteman Cancer Center OnCore Database

All patients must be registered through the Siteman Cancer Center OnCore database. Registration in the SCC database will be the last step of the patient registration process. Once the patient has been registered in the SCC database, s/he will be considered registered to the study.

4.3 Assignment of UPN

Each patient will be identified with a unique patient number (UPN) for this study. All data will be recorded with this identification number on the appropriate CRFs.

5.0 TREATMENT PLAN

5.1 Study Summary

5.1.1 Arm A

Six patients enrolled to this study will be in Arm A; patients may be enrolled to Arm A at any time throughout the lifetime of the study. Arm A patients will undergo MLA and will be followed with standard of care therapy at the discretion of the treating physician.

Arm A patients will undergo DSC and DCE-MRI at the following time points along with standard of care imaging:

- no more than 3 weeks prior to MLA (OPTIONAL)
- within approximately 4 days after MLA
- 2-4 weeks after MLA
- Every 12 weeks (+/- 7 days) for the first year or until disease progression (see Section 9.1)

Arm A patients will have 7 ml of blood drawn at the following time points:

- Before MLA; this sample can be collected any time during the 3 days before or the day of the procedure until the start of the procedure
- Within approximately 3 days after MLA
- 2-4 weeks (+/- 3 days) after MLA (at time of DSC/DCE-MRI)
- Every 12 weeks (+/- 7 days) at time points correlating with MRIs for the first year or until disease progression

The purpose of these blood draws is to measure serum levels of brain-specific factors (S100B, GFAP, and BSE) and cytokine levels. PBMC (for the pre- and post-MLA samples) will also be isolated to determine the phenotypes and functions of peripheral blood immune cells following MLA (see Section 9.2-9.4).

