1.0 BACKGROUND AND RATIONALE

1.1 Pediatric Brain Tumors

Pediatric brain tumors comprise a heterogeneous group of tumors, including gliomas (high and low grade), medulloblastoma, ependymoma, primitive neuroectodermal tumor (PNET), atypical teratoid/rhabdoid tumor (ATRT), choroid plexus carcinoma, as well as other rarer tumors. Gliomas are the most common tumors in pediatrics, especially grade I (pilocytic astrocytoma) and grade II. High grade gliomas include anaplastic astrocytoma, glioblastoma (GBM), and mixed oligoastrocytomas. As with adults, high grade gliomas in pediatrics confer a poor prognosis. The current standard chemoradiotherapy for newly diagnosed high grade glioma produces only a modest survival benefit in pediatric patients, with less than 20% alive at five years [1]. All recurrent pediatric malignant tumors have a very poor prognosis with no standard and few effective therapeutic options available. Most children with relapsed disease will succumb within 3 years of recurrence with any malignant tumors. One of the challenges in treating brain tumors is the limitation of many agents to penetrate the blood brain barrier (BBB). Several methods to overcome BBB disruption have been attempted and currently undergoing studies, including intra-arterial chemotherapy administration, direct intratumoral/intracavitary placement of chemotherapy agents, and convection-enhanced delivery of agents, although a method with clear survival benefit has yet to be demonstrated [2].

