1.3.1 Prior Clinical Experience with MLA

We have had one of the largest clinical experiences using MLA in the country. To date we have done more than 80 cases, of which approximately two-thirds are high-grade glial neoplasms. In regards to adverse events, patients have experienced transient aphasia, transient hemiparesis, transient hyponatremia, and a documented case of lower extremity deep venous thrombosis. Patients with aphasia or hemiparesis improved over time with steroid therapy. Hyponatremia resolved spontaneously. One patient experienced fatal meningitis. Subsequent in-depth analysis revealed that this patient's meningitis was due to an operating room infrastructure-related contamination and not due to equipment contamination related to performance of the MLA procedure.

1.4 MLA followed by Standard of Care in Newly Diagnosed Glioma Patients (Arm A)

MLA offers an alternative to some patients with tumors that are unresectable. Complete surgical resection of grade I and II gliomas have a >90% overall survival, although complete resection is not always possible due to the location of the tumor. For tumors with less than a complete resection, chemotherapy or radiation therapy is offered for progressive

and/or symptomatic tumors. For high grade gliomas, patients who have a complete resection of the enhancing tumor at time of diagnosis [29, 30] or at relapse have a longer survival compared to those with residual disease [31]. In this arm of the study, patients with any grade glioma who are candidates for MLA will undergo this procedure followed by standard of care treatment.

1.5 MLA followed by Doxorubicin and Etoposide in Relapsed Malignant Tumor Patients (Arm B)

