2.0 OBJECTIVES

2.1 Primary Objectives

1. To determine progression-free survival (PFS) and overall survival (OS) of patients with new diagnosis glioma who are candidates for MLA (Arm A).
2. To determine 6-month progression-free survival (6PFS) in patients who receive doxorubicin immediately following MLA and low-dose etoposide as maintenance therapy in patients who are candidates for MLA with any type relapsed malignant brain tumors (Arm B).
3. To evaluate quality of life (QOL) using Karnofsky or Lansky performance status in patients following MLA and in patients who receive doxorubicin and maintenance etoposide after MLA.

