3.0 PATIENT SELECTION

3.1 Inclusion Criteria – Arm A

1. Presumed pediatric gliomas (grades I-IV) on MRI that are determined to be candidates for MLA by the treating neurosurgeon.
2. Age 3 to \leq 21
3. Karnofsky/Lansky performance status \geq 60%, see Appendix 1.

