5.9 Duration of Follow-up

Patients in Arm A will be followed every 12 weeks after the 6-week (or 10-week if done) post-MLA scan until 1 year has elapsed since patient registration or until death, whichever occurs first. Following the first year, patients will continue to be followed every 6 months or at event occurrence for 5 years after patient registration or until death, whichever occurs first. Patients in Arm B will be followed every 8 weeks after the 6-week (or 10-week if done) post-MLA scan until 2 years have elapsed since patient registration or until progression, whichever occurs first. Following the first two years, patients will continue to be followed every 6 months or at event occurrence for 5 years after patient registration or until death, whichever occurs first. Follow-up consists of collection of Karnofsky performance status, DSC/DCE-MRI, and blood for biomarkers until disease progression (or 2 years of elapsed since patient registration or death, whichever occurs first). After documented disease progression, vital status and subsequent treatment will be obtained every 12 weeks for the remainder of the 2 years or until death, whichever occurs first. Patients removed from study for unacceptable adverse events that are possibly, probably, or definitely related to study procedures will be followed until resolution or stabilization of the adverse event. "Stabilization" is defined as remaining at a consistent CTCAE version 4.0 grade of the event for two consecutive assessments.

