10.0 STUDY CALENDAR

10.1 Arm A Study Calendar

	Baseline ¹	MLA	3 Days Post-MLA	2-4 Weeks Post-MLA	Every 12 Wks Thereafter for 12 months Post-MLA ⁴	F/U ¹⁰
Informed consent	X					
Medical history	X					
Physical exam incl. wt	X		X ³	X	X ⁹	X ¹¹
Karnofsky/Lansky	X		X	X	X ⁹	X ¹¹
CBC	X					
CMP	X					
Urine or serum β HCG	X ⁷					
MRI with DCE/DSC	X ⁸		X ²	X ²	X ⁹	X ¹¹
Biopsy		X ⁸				
Blood to measure brain-specific factors (Sections 9.2-9.4)	X		X ²	X ²	X ⁹	X ¹¹
Adverse event assessment ⁵		X	X	X	X	X

1. No more than 21 days prior to MLA.

2. +/- 3 days

3. Weight not required

4. Patients will be followed every 12 weeks from the Week 4 MRI until 1 year has elapsed since MLA or progression, whichever occurs first. After progression, vital status and subsequent treatment will be recorded.

5. Through one year or off protocol.

6. To be obtained with MRI.

7. Females of childbearing potential

8. Optional

9. +/- 7 days

10. F/U every 6 months or at event occurrence for 5 years or until death, whichever occurs first

11. +/- 2 weeks

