14.0 STATISTICAL CONSIDERATIONS

Since we do not have any preliminary data for MR imaging, serum biomarkers, etc, it is not feasible to estimate sample size or provide power estimates. Therefore, this study is considered as a pilot study and the data collected will be used to design future studies. We propose six patients each arm as this is considered to be reasonable to recruit within the available a time frame.

In each arm, we will consider the following statistical analysis:

For the primary endpoint, MR imaging will be collected at the time points: pre-MLA (OPTIONAL), post-MLA, two-four weeks after MLA and every twelve weeks in Arm A; pre-MLA, post-MLA, two-four weeks after MLA and every eight weeks in Arm B. The linear regression model will used to investigate the correlation between MR imaging and peritumoral BBB disruption. To account for correlation among the repeated measures from the same patient, the longitudinal data will be analyzed with the use of linear generalized estimating equation (GEE). Whether the average measurements differ at the multiple time points will be evaluated through GEE model. Least-square means at each time points will be presented and standard errors will be calculated within the use of the GEE sandwich method when accounting for within-patient correlation.

Since we do not know which biomarkers will have better correlation with the Ktrans data from DCE and DSC-MRI and patients' survival outcome, we plan to determine the levels of all 3 biomarkers in a blinded fashion. Once both the Ktrans and biomarker levels are available, we will determine which biomarkers have the closest correlation that is statistically significant with the Ktrans. Pearson correlation coefficient (r) will be determined for each biomarker and Ktrans value. Biomarkers with higher correlation coefficient (r approaching 1) will be given higher priority. A minimum $r=0.5$ is required for inclusion for further analysis and will be used as a peritumoral

permeability score. This score will then be correlated with the patient outcome data (as measured by 6PFS rate) to determine whether it has a predictive value.

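### Arm A: conflicting end dates for imaging and survival follow-up make PFS and OS beyond year 1 depend on the section followed, and pooling grades I to IV makes the curves depend on grade mix

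*Combined protocol and SAP*

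**What the plan says.** Section 2.1 makes this a primary objective: "To determine progression-free survival (PFS) and overall survival (OS) of patients with new diagnosis glioma who are candidates for MLA (Arm A". It names no time point. Section 12.3.6 measures PFS from treatment start to the earlier of progression and death. Neither that section nor Section 14 says when an event-free patient is censored.

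The end of Arm A imaging is described in five places:

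| Section | Arm A MRI or response assessment |
|---|---|
| 5.1.1 | "Every 12 weeks (+/- 7 days) for the first year or until disease progression (see Section 9.1" |
| 9.1 | Same: 12-weekly, first year or progression |
| 5.9 | Follow-up content includes "DSC/DCE-MRI, and blood for biomarkers until disease progression (or 2 years of elapsed since patient registration or death, whichever occurs first"; the sentence comes after the Arm B text but names no arm |
| 10.1 | 12-weekly to one year or progression (footnote 4); the MRI row is then also marked in the F/U column, which footnote 10 defines as "F/U every 6 months or at event occurrence for 5 years or until death, whichever occurs first" |
| 12.1 | Response re-evaluated 12-weekly, no end stated |

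Survival follow-up is described in three ways. Sections 5.9 and 10.1 give five years. Section 5.9 also says that, once progression is documented, vital status is collected 12-weekly only until two years are complete. The Section 11.0 Follow Up Form for Arm A stops one year after MLA.

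On population, Section 3.1 admits "Presumed pediatric gliomas (grades I-IV) on MRI that are determined to be candidates for MLA by the treating neurosurgeon". Section 1.4 says "Complete surgical resection of grade I and II gliomas have a >90% overall survival", and Section 1.1 describes newly diagnosed high-grade glioma "with less than 20% alive at five years". Section 14 plans Kaplan-Meier curves for each arm without grade strata, and a log-rank test of Arm A OS against a historical control given bevacizumab only. The sample size is a feasibility figure: "We propose six patients each arm as this is considered to be reasonable to recruit within the available a time frame".

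**The concern.** There are two separate problems.

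First, the observation window. A patient whose last study scan is at month 12 and who is alive without known progression at year 4 could enter the PFS analysis as censored at 1 year or as progression-free to 4 years. Either treatment can be defended from the text. Similarly, deaths after year 1, or after year 2 in patients who have progressed, may or may not be captured, depending on which follow-up rule is applied.

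Second, the mixture. Arm A puts tumours with very different expected courses into one curve of six patients, and a formal comparison is planned on that curve. Section 14 says the data will be used to design later studies. A pooled estimate that depends heavily on who happened to enrol is a poor planning input unless the grade of each patient is reported beside it.

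**Working it through.** The plan states no power, alpha, effect size or event count for Arm A, so there is no figure to reproduce. The numbers below only show the scale.

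**1. Effect of the missing censoring rule (hypothetical).** Suppose three of six patients progress within year 1 and three are event-free at their month-12 scan. Kaplan-Meier PFS is then 3/6 = 50%. Censored at the last scan, the curve ends at month 12. Censored at last contact, it stays flat at 50% for as long as contact continues, and could be read as 5-year PFS of 50% with no scan after month 12. The exact 95% interval for 3 of 6 is 12% to 88%.

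**2. How many low-grade events fall after each end date.** The documents give no low-grade PFS. Assume a constant hazard and 5-year PFS (S5) between 40% and 80%. The share of five-year events occurring by year t is (1 - S5^(t/5)) / (1 - S5).

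| S5 | by year 1 | after year 1 | by year 2 | after year 2 |
|---|---|---|---|---|
| 0.4 | 28% | 72% | 51% | 49% |
| 0.6 | 24% | 76% | 46% | 54% |
| 0.8 | 22% | 78% | 43% | 57% |

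**3. Whether a median PFS is reached.** Assume 5-year PFS of 50-70% in low grade and 1-year PFS of 30-40% in high grade, both exponential. The table gives expected events among six patients and the exact chance of at least three events.

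| High-grade patients | Horizon | Expected events | Chance of 3 or more |
|---|---|---|---|
| 3 of 6 | 1 year | 2.0-2.5 | 30-50% |
| 3 of 6 | 2 years | 2.9-3.5 | 71-88% |
| 3 of 6 | 5 years | 3.9-4.5 | about 99-100% |
| 0 of 6 | 1 year | 0.4-0.8 | 1-3% |
| 0 of 6 | 2 years | 0.8-1.5 | 3-16% |
| 0 of 6 | 5 years | 1.8-3.0 | 26-66% |

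So whether a median exists at all can turn on the end date used. The 3- and 6-month estimates do not: every version scans 12-weekly in year 1, so the end date cannot move them.

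**4. Grade mix and OS.** Take 90% and 20% as 5-year survival for low and high grade. This is an assumption: the 90% figure is a lower bound for completely resected tumours with no time horizon, and the 20% figure is an upper bound. With k high-grade patients, pooled 5-year OS = [(6 - k) x 0.90 + k x 0.20] / 6.

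| k | 0 | 1 | 2 | 3 | 4 | 5 | 6 |
|---|---|---|---|---|---|---|---|
| Pooled 5-year OS | 90% | 78% | 67% | 55% | 43% | 32% | 20% |

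Each patient swapped moves the estimate by 0.70/6 = 11.7 points. Expected deaths by 5 years run from 6 x 0.10 = 0.6 to 6 x 0.80 = 4.8, so grade mix alone could shift the log-rank comparison greatly. With exponential curves through the same anchors, pooled OS ranges from 98% to 73% at 1 year and from 99% to 85% at 6 months. The early landmarks therefore depend on mix too, but less.

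**The case against.** The strongest reply is that this is a declared pilot: no power is claimed, the objective names its population, and Sections 5.9 and 10.1 can be read together as 12-weekly assessment in year 1 and six-monthly assessment to year 5. On that reading, Sections 5.1.1 and 9.1 limit only the permeability sequences, which are added to routine imaging, and disease response is governed by Section 12.1. This is a sensible reading, but no section states it. Section 10.1 marks the DCE/DSC MRI row itself in the F/U column, so the sequences still conflict. The mark is not an obvious template carry-over either, because the Arm B calendar leaves the same cell empty.

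Several stronger conclusions that a reader might draw are not supported:

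- **That the end of imaging alters OS.** It does not. OS is affected only through the conflicting vital-status periods.
- **That two years is a firm third end date.** The sentence may be meant for Arm B, whose imaging horizon is two years. Without it, one year against five remains.
- **That different sites would follow different sections.** The documents describe one centre. The ambiguity lies with the study team and the analyst.
- **That late progression would go unassessed.** The calendar provides six-monthly examination, performance status and MRI. The trouble is that other sections disagree with it.
- **That grade will be unknown because biopsy is optional.** Section 9.5 concerns immune testing and refers to tissue used for histologic diagnosis, so grade may be available for many patients.

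It is also fair that six patients split by grade will not support useful separate curves. Labelled individual times avoid that problem.

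**Conclusion.** The point holds in a limited form. The one-year against five-year conflict on Arm A imaging is plain on the page, and nothing elsewhere, including a censoring rule, resolves it. It affects PFS beyond year 1 and any late median, and leaves the 3- and 6-month estimates that Section 14 offers as examples untouched. OS has a separate conflict between one-, two- and five-year vital-status collection.

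Pooling grades I to IV is acceptable for enrolment in a pilot. What does not stand is a pooled curve as the main result, or a log-rank conclusion drawn from it: Section 14 makes no grade adjustment and does not describe the grade composition of the control.

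The direction of these effects follows from the documents. Their size does not. The 72-78% of low-grade events after year 1 rests on an assumed 40-80% 5-year PFS and constant hazard. The 12 points per patient would be misread as the protocol's own estimate, since it gives a complete-resection figure a 5-year horizon and Section 1.4 presents MLA as an alternative for some patients whose tumours cannot be resected. This should be corrected, but it does not undermine the pilot.

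**What to change.** 1. **Follow-up.** Reconcile Sections 5.1.1, 5.9, 9.1, 10.1, 11.0 and 12.1 to one Arm A disease-assessment end date and one vital-status period, and state which arm the 2-year sentence in 5.9 covers. Extend or end the Follow Up Form to match.
2. **PFS rule.** In Sections 12.3.6 and 14, count death and clinical progression as events alongside radiological progression. Censor event-free patients at the last adequate disease assessment, not at last contact. Censoring on MRI alone would be wrong, because the Section 12.1 criteria accept clear clinical deterioration as progression. Quote PFS only up to the agreed horizon.
3. **Reporting.** In Section 14, list Arm A PFS and OS as patient-level times labelled grade I-II, grade III-IV or not histologically confirmed. Make any pooled curve secondary and descriptive, and draw no conclusion from the pooled log-rank test against the historical control.

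The cost is mainly wording. If the agreed imaging date is five years, the calendar already implies up to 2 x 4 = 8 scans per patient after year 1, or 48 for six patients, fewer with progression or death; some may coincide with routine scans. If it is earlier, the cost is a shorter PFS horizon. The grade-group results will be descriptive, with very few patients in each.
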